**<each group>:**

RSV-Ld = Low dose ChAd155-RSV vaccine (5 x 10^9 vp)  
 RSV-Md = Middle dose ChAd155-RSV vaccine (1.5 x 10^10 vp)  
 RSV-Hd = High dose ChAd155-RSV vaccine (5 x 10^10 vp)  
 Placebo-Ld = Non-active control (0.5 ml)

Placebo-Md = Non-active control (0.15 ml)

Placebo-Hd = Non-active control (0.5 ml)

For each dose:

N = number of subjects with the corresponding documented dose

n/% = number/percentage of subjects reporting the symptom at least once following the corresponding dose

For Overall/dose:

N = number of documented dose

n/% = number/percentage of doses followed by at least one type of symptom

For Overall/subject:

N = number of subjects with at least one documented dose

n/% = number/percentage of subjects reporting the type of symptom at least once

95%CI= Exact 95% confidence interval; LL = lower limit, UL = upper limit

Temperatures were coded as follows:

1:  $\geq 37.5$  °C to  $\leq 38.5$  °C

2:  $> 38.5$  °C to  $\leq 39.5$  °C

3:  $> 39.5$  °C

**Template 20 Incidence of solicited general symptoms reported during the 7-day (Days 1-7) post-vaccination period following each dose and overall by maximum grading <Exposed Set>**

Dose	Symptom	Type	Each group					
			N	n	%	LL	UL	
DOSE 1	Drowsiness	All						
		Grade 1						
		Grade 2						
		Grade 3						
		Related						
		Grade 2 Related						
		Grade 3 Related						
		Medical advice						
	Irritability / Fussiness	All						
		Grade 1						
		Grade 2						
		Grade 3						
		Related						
		Grade 2 Related						
		Grade 3 Related						
		Medical advice						
	Loss Of Appetite	All						
		Grade 1						
		Grade 2						
		Grade 3						
		Related						
		Grade 2 Related						
		Grade 3 Related						
		Medical advice						
	Temperature/(Axillary) (°C)	All						
		≥37.5 - ≤38.5						
		>38.5 - ≤39.5						
		>39.5						
		Related						
		>38.5 - ≤39.5*Related						
		>39.5*Related						
		Medical advice						
		DOSE 2	Drowsiness	All				
				Grade 1				
	Grade 2							
	Grade 3							
Related								
Grade 2 Related								
Grade 3 Related								
Medical advice								
Irritability / Fussiness	All							
	Grade 1							
	Grade 2							
	Grade 3							
	Related							
	Grade 2 Related							
	Grade 3 Related							
	Medical advice							

Dose	Symptom	Type	Each group					
			N	n	%	LL	UL	
	Loss Of Appetite	All						
		Grade 1						
		Grade 2						
		Grade 3						
		Related						
		Grade 2 Related						
		Grade 3 Related						
		Medical advice						
	Temperature/(Axillary) (°C)	All						
		≥37.5 - ≤38.5						
		>38.5 - ≤39.5						
		>39.5						
		Related						
		>38.5 - ≤39.5*Related						
		>39.5*Related						
		Medical advice						
	OVERALL/DOSE	Drowsiness	All					
			Grade 1					
Grade 2								
Grade 3								
Related								
Grade 2 Related								
Grade 3 Related								
Medical advice								
Irritability / Fussiness		All						
		Grade 1						
		Grade 2						
		Grade 3						
		Related						
		Grade 2 Related						
		Grade 3 Related						
		Medical advice						
Loss Of Appetite		All						
		Grade 1						
		Grade 2						
		Grade 3						
		Related						
		Grade 2 Related						
		Grade 3 Related						
		Medical advice						
Temperature/(Axillary) (°C)	All							
	≥37.5 - ≤38.5							
	>38.5 - ≤39.5							
	>39.5							
	Related							
	>38.5 - ≤39.5*Related							
	>39.5*Related							
	Medical advice							
OVERALL/SUBJECT	Drowsiness	All						
		Grade 1						
		Grade 2						
		Grade 3						
		Related						

Dose	Symptom	Type	Each group				
			N	n	%	LL	UL
		Grade 2 Related					
		Grade 3 Related					
		Medical advice					
	Irritability / Fussiness	All					
		Grade 1					
		Grade 2					
		Grade 3					
		Related					
		Grade 2 Related					
		Grade 3 Related					
		Medical advice					
		Loss Of Appetite	All				
	Grade 1						
	Grade 2						
	Grade 3						
	Related						
	Grade 2 Related						
	Grade 3 Related						
	Medical advice						
	Temperature/(Axillary) (°C)		All				
		≥37.5 - ≤38.5					
		>38.5 - ≤39.5					
		>39.5					
		Related					
		>38.5 - ≤39.5*Related					
		>39.5*Related					
		Medical advice					

RSV-Ld = Low dose ChAd155-RSV vaccine (5 x 10^9 vp)  
 RSV-Md = Middle dose ChAd155-RSV vaccine (1.5 x 10^10 vp)  
 RSV-Hd = High dose ChAd155-RSV vaccine (5 x 10^10 vp)  
 Placebo-Ld = Non-active control (0.5 ml)  
 Placebo-Md = Non-active control (0.15 ml)  
 Placebo-Hd = Non-active control (0.5 ml)

For each dose:

N = number of subjects with the corresponding documented dose  
 n/% = number/percentage of subjects reporting the type of symptom as maximum intensity during the follow-up period

For Overall/dose:

N = number of documented dose  
 n/% = number/percentage of doses followed by the type of symptoms as maximum intensity during the follow-up period

For Overall/subject:

N = number of subjects with at least one documented dose  
 n/% = number/percentage of subjects reporting the type of symptoms as maximum intensity during the follow-up period

95%CI = Exact 95% confidence interval; LL = lower limit, UL = upper limit

Temperatures were coded as follows:

- 1: ≥ 37.5 °C to ≤ 38.5 °C
- 2: > 38.5 °C to ≤ 39.5 °C
- 3: > 39.5 °C

**Template 21 Maximum Temperature reported during the 7-day (Days 1-7) post-vaccination period – dose X <Exposed Set>**

		Each group N =				Total N =			
				95% CI				95% CI	
Characteristics	Categories	n	%	LL	UL	n	%	LL	UL
Maximum temperature	No fever								
	Unknown temperature								
	[37.5-37.9]								
	[38.0-38.4]								
	[38.5-38.9]								
	[39.0-39.4]								
	[39.5-39.9]								
	[40.0-....								

N = number of subjects with documented dose  
 n/% = number/percentage of subjects in a given category  
 95%CI = Exact 95% confidence interval; LL = lower limit, UL = upper limit

**Template 22 Percentage of subjects reporting the occurrence of unsolicited symptoms classified by MedDRA Primary System Organ Class and Preferred Term within the 30-day (Days 1-30) post-vaccination period <Exposed Set>**

		Each group N =			
				95% CI	
Primary System Organ Class (CODE)	Preferred Term (CODE)	n	%	LL	UL
At least one symptom					
Gastrointestinal disorders (10017947)	Diarrhoea (10012735)				
	Teething (10043183)				
	Vomiting (10047700)				
General disorders and administration site conditions (10018065)	Pyrexia (10037660)				
Immune system disorders (10021428)	Seasonal allergy (10048908)				
Infections and infestations (10021881)	Conjunctivitis (10010741)				
	Otitis media (10033078)				
	Paronychia (10034016)				
	Tonsillitis (10044008)				
	Tonsillitis streptococcal (10044013)				
	Viral upper respiratory tract infection (10047482)				
Injury, poisoning and procedural complications (10022117)	Arthropod bite (10003399)				
	Face injury (10050392)				
	Head injury (10019196)				
Skin and subcutaneous tissue disorders (10040785)	Miliaria (10027627)				

RSV-Ld = Low dose ChAd155-RSV vaccine (5 x 10^9 vp)  
 RSV-Md = Middle dose ChAd155-RSV vaccine (1.5 x 10^10 vp)  
 RSV-Hd = High dose ChAd155-RSV vaccine (5 x 10^10 vp)  
 Placebo-Ld = Non-active control (0.5 ml)  
 Placebo-Md = Non-active control (0.15 ml)  
 Placebo-Hd = Non-active control (0.5 ml)  
 At least one symptom = at least one symptom experienced (regardless of the MedDRA Preferred Term)  
 N = number of subjects included in the considered cohort in each group  
 n/% = number/percentage of subjects reporting the symptom at least once  
 95% CI = exact 95% confidence interval; LL = Lower Limit, UL = Upper Limit

**Template 23 Number and percentage of subjects taking a concomitant medication during the 7- day (Days 1-7) post -vaccination period <Exposed Set>**

		<each group>				
		N	n	%	95% CI	
Dose	Type				LL	UL
DOSE 1	Any					
	Any antipyretics					
	Prophylactic antipyretics					
DOSE 2	Any					
	Any antipyretics					
	Prophylactic antipyretics					
OVERALL/DOSE	Any					
	Any antipyretics					
	Prophylactic antipyretics					
OVERALL/SUBJECT	Any					
	Any antipyretics					
	Prophylactic antipyretics					

**<each group>:**

RSV-Ld = Low dose ChAd155-RSV vaccine (5 x 10^9 vp)  
 RSV-Md = Middle dose ChAd155-RSV vaccine (1.5 x 10^10 vp)  
 RSV-Hd = High dose ChAd155-RSV vaccine (5 x 10^10 vp)  
 Placebo-Ld = Non-active control (0.5 ml)  
 Placebo-Md = Non-active control (0.15 ml)  
 Placebo-Hd = Non-active control (0.5 ml)

For each dose:

N = total number of subjects with the corresponding administered dose  
 n/% = number/percentage of subjects took the specified type of concomitant medication at least once during the considered period

For Overall/dose:

N = number of administered doses  
 n/% = number/percentage of doses after which the specified type of concomitant medication was taken at least once during the considered period

For Overall/subject:

N = total number of subjects with at least one administered dose  
 n/% = number/percentage of subjects who took the specified type of concomitant medication at least once during the considered period

95%CI = Exact 95% confidence interval; LL = lower limit, UL = upper limit

**Template 24 Distribution of change from baseline in hematology and biochemistry with respect to normal laboratory ranges <Exposed Set>**

Laboratory parameter	Timing	Range indicator at Baseline (SCR)	Range indicator at timing	<each group >		
				N	n	%
Alanine Aminotransferase	PI(D2)	Unknown	Unknown			
			Below			
			Within			
			Above			
		Below	Unknown			
			Below			
			Within			
			Above			
		Within	Unknown			
			Below			
			Within			
			Above			
		Above	Unknown			
			Below			
			Within			
			Above			
	PI (D8)	...				
	PI (D31)					
	PII (D32)	...				
	PII (D38)	...				
	PII (D61)	...				
	UNSCH1					
	UNSCH2					
	...	...				
Aspartate Aminotransferase	...	...				
Creatinine	...	...				
Hemoglobin						
Leukocytes (White Blood Cells)	...	...				
Neutrophil						
Platelets	...	...				

**<each group>:**

RSV-Ld = Low dose ChAd155-RSV vaccine (5 x 10^9 vp)  
 RSV-Md = Middle dose ChAd155-RSV vaccine (1.5 x 10^10 vp)  
 RSV-Hd = High dose ChAd155-RSV vaccine (5 x 10^10 vp)  
 Placebo-Ld = Non-active control (0.5 ml)  
 Placebo-Md = Non-active control (0.15 ml)  
 Placebo-Hd = Non-active control (0.5 ml)  
 N = number of subjects with available results for the specified laboratory parameter and timing in a given baseline category  
 n/% = number/percentage of subjects in the specified category  
 Below = below the normal laboratory range defined for the specified laboratory parameter  
 Within = within the normal laboratory range defined for the specified laboratory parameter  
 Above = above the normal laboratory range defined for the specified laboratory parameter  
 SCR= Screening  
 PI (D2): Post-vaccination dose 1 at Day 2  
 PI (D8): Post-vaccination dose 1 at Day 8  
 PI (D31): Post-vaccination dose 1 at Day 31  
 PII (D32): Post-vaccination dose 2 at Day 32  
 PII (D38): Post-vaccination dose 2 at Day 38

PII (D61): Post-vaccination dose 2 at Day 61  
 UNSCH: Unscheduled visit for safety

**Template 25 Summary of hematology and biochemistry results by maximum grade from VISIT X (DX) up to VISIT Y (DY) – post dose 1 of vaccination versus baseline <Exposed Set>**

Laboratory parameter	Baseline (SCR)	Visit 2 to Visit X	<each group >		
			N	n	%
Hemoglobin (decrease)	Unknown	Unknown			
		Grade 0			
		Grade 1			
		Grade 2			
		Grade 3			
		Grade 4			
	Grade 0				
	Grade 1				
	Grade 2				
	Total				
Leukocytes (White Blood Cells) (decrease)	...				
Neutrophil (decrease)					
Platelets					
Alanine Aminotransferase					
Aspartate Aminotransferase					
Creatinine					

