testing will be performed on that day. Further testing may be required to investigate a finding or guide subject management based on the investigators clinical judgment. Subjects' parent(s)/LAR(s) will be instructed to contact the investigator/study staff if their child presents symptoms of spontaneous bleeding or easy bruising or if their child develops a rash in the month following vaccination, in order to detect any thrombocytopenic petechiae or purpura. The investigator will, based on his/her medical judgement, appropriately investigate infants with clinical suspicion of low platelets.

- Refer to Section 6.6.11.2 and Figure 2 for information about the re-testing of samples in case of any Grade 1 abnormality with potential clinical relevance or any \geq Grade 2 abnormality.
- Blood sample for **RSV serostatus** will be taken from all infants at Screening.
- Blood samples for **CMI** are limited to those in investigational sites with a laboratory in proximity capable to perform WBS necessary for the CMI assay. In those sites, samples will be taken from all subjects at Screening and on Day 30, Day 60, and Day 365.

Note: Blood samples for CMI taken on Day 7 and Day 37 for subjects enrolled under protocol amendment 1 will still be assessed for CMI.

- Blood samples for **humoral immunogenicity** will be taken from all subjects at Screening and on Day 30, Day 60, and Day 365.
 - Blood sample for **assessment of mechanism of illness (potential ERD)** will be taken from subjects hospitalized for LRTI (only for RSV-positive subjects using a locally available RSV test).
 - Nasal swab: there will be monthly nasal swab to detect asymptomatic RSV infections during the RSV season and if following active or a passive surveillance contacts, a subject presents symptoms of RTI, a nasal swab will be collected.

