Blood samples for biochemistry will be taken from all infants at Screening (up to 29 days before first vaccination to Day 1) and on Day 31, and Day 61 (refer to Table 11 of the protocol for the list of parameters to be tested). Blood samples for hematology will be taken from all infants at Screening (up to 29 days before first vaccination to Day 1) and on Day 1, Day 31, Day 32, and Day 61 (refer to Table 11 of the protocol for the list of parameters to be tested). Day 8 hematology testing will be performed if any  $\geq$  Grade 1 for platelet decrease is detected on Day 2 after vaccination, to ensure its resolution. Similarly, hematology testing on Day 38 will be performed if any  $\geq$  Grade 1 for platelet decrease is detected on Day 32. A clinical examination with special attention given to detection of spontaneous bleeding or easy bruising and evidence of bruising or petechiae will be performed by the investigator/study staff on Day 2, Day 4 and Day 8 after each vaccination (i.e. Day 2, Day 4, Day 8, Day 32, Day 34, and Day 38. The visits on Day 4 and Day 34 may be replaced by a phone call by the investigator/study staff to inquire of the infants' general health and to solicit reports of a rash, spontaneous bleeding or easy bruising. On Day 2, and Day 32, special attention will also be given to the detection of petechiae or evidence of petechiae induced by the tourniquet. This special attention to detection of petechiae or evidence of petechiae induced by the tourniquet will also be given on Day 8 and/or Day 38 in case hematology testing will be performed on that day. Further testing may be required to investigate a finding or guide subject management based on the investigators clinical judgment. Subjects' parent(s)/LAR(s) will be instructed to contact the investigator/study staff if their child presents symptoms of spontaneous bleeding or easy bruising or if their child develops a rash in the month following vaccination, in order to detect any thrombocytopenic petechiae or purpura. The

investigator will, based on his/her medical judgement, appropriately investigate infants with clinical suspicion of low platelets

- Blood sample for **RSV serostatus** will be taken from all infants at Screening.

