### **4. ENDPOINTS**

#### **4.1. Primary endpoints**

- Occurrence of AEs from first vaccination (Day 1) up to Day 61.
  - Occurrence of each solicited local and general AE, during a 7-day follow-up period after each vaccination (i.e. the day of vaccination and 6 subsequent days).
  - Occurrence of any unsolicited AE, during a 30-day follow-up period after each vaccination (i.e. the day of vaccination and 29 subsequent days).

- Occurrence of any SAE from Day 1 up to Day 61.
- Occurrence of episode of spontaneous or excessive bleeding (AE of specific interest), during a 30-day follow-up period after each vaccination.
- Occurrence of any hematological (hemoglobin level, white blood cells and platelets) laboratory abnormalities at Screening, Day 1, Day 8, Day 31, Day 32, Day 38, and Day 61.
- Occurrence of any biochemical (alanine aminotransferase, aspartate aminotransferase and creatinine) laboratory abnormalities at Screening, Day 31, and Day 61

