The percentage of subjects with unsolicited AEs within 30 days (Day 1-30) after each vaccine dose (overall doses) with its exact 95% CI will be tabulated by group and by MedDRA preferred term. Similar tabulation will be done for Grade 3 unsolicited AEs, for any causally related unsolicited AEs, for Grade 3 causally related unsolicited AEs and for unsolicited AEs resulting in a medically attended visit. The verbatim reports of unsolicited AEs will be reviewed by a physician and the signs and AEs will be coded according to the MedDRA Dictionary Version 20 for Adverse Reaction Terminology. Every verbatim term will be matched with the appropriate Preferred Term.

The percentage of subject with episode of spontaneous or excessive bleeding (AE of specific interest), during a 30-day follow-up period after each vaccination will be tabulated by group according to associated PT code presented in Section 12. The percentage of subjects with RSV-LRTI (AE of specific interest) from Dose 1 up to Day 365 and from Dose 1 up to study conclusion (Day 730) will be tabulated by group according to associated PT code presented in Section 12.

The percentage of subjects with SAE within 30 days (Day 1-30) after each vaccine dose with its exact 95% CI will be tabulated by group and by MedDRA preferred term. Similar table will be generated for SAE from Dose 1 up to Day 61, from Dose 1 up to Day 366 and from Dose 1 up to Day 731.

SAEs reported throughout the study and AE of specific interest will be described in detail.

The percentage of subjects using concomitant medication (any medication, any antipyretic/ analgesic and any antipyretic taken prophylactically, respectively) during the 7-day follow-up period (Day 1-7) and during the 30-day follow-up period (Day 1-30) will be summarized by group after each vaccine dose and overall.

For each group and for each hematology and biochemistry parameter:

- The percentage of subjects having hematology and biochemistry results below/above/within the local laboratory normal ranges will be tabulated by timepoint and toxicity grading scale.
- The maximum grading from Screening up to Visit 9 (Day 61) will be tabulated by grading the safety laboratory values according to toxicity criteria Grading scale adapted from [Division of AIDS, 2003], [Division of AIDS, 2004] and [Division of AIDS, 2007].

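### Day 8 and Day 38 platelet percentages in Template 24 are based only on infants tested because of a recent platelet drop, so they overstate the group rate

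*SAP*

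**What the plan says.** SAP days are protocol days plus one, so SAP Days 2, 8, 32 and 38 are protocol Days 1, 7, 31 and 37.

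- **Sampling rule.** In SAP section 2 (sampling schedule), Day 8 haematology is done when at least "Grade 1 for platelet decrease is detected on Day 2 after vaccination, to ensure its resolution", and Day 38 haematology when at least "Grade 1 for platelet decrease is detected on Day 32". Protocol sections 3 and 6.6.11.2 give the same rule.
- **Endpoint.** SAP section 4.1 lists, as a primary endpoint component, haematological "laboratory abnormalities at Screening, Day 1, Day 8, Day 31, Day 32, Day 38, and Day 61". The two conditional visits stand beside visits sampled in all infants.
- **Analysis.** SAP section 6.4.1.1: "The percentage of subjects having hematology and biochemistry results below/above/within the local laboratory normal ranges will be tabulated by timepoint and toxicity grading scale". It has no separate rule for the conditional visits.
- **Table shell.** Template 24 has D8 and D38 rows next to D2, D31, D32 and D61, with the base "N = number of subjects with available results for the specified laboratory parameter and timing in a given baseline category". Its footnote marks unscheduled safety visits as such, but does not mark D8 and D38 as triggered. Template 26 (eosinophils, basophils, monocytes) also has D8 and D38 rows based on available results.
- **Earlier sampling.** Protocol section 3 refers to "Blood samples for CMI taken on Day 7 and Day 37 for subjects enrolled under protocol amendment 1". That note concerns cell-mediated immunity only. The Amendment 2 entry in protocol Appendix D shows that platelet counts were also routine on those two days until that amendment (08 June 2017) made them conditional. SAP section 9 (changes from planned analyses) does not mention this.

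**The concern.** A by-timepoint percentage is normally read as the state of the group at that visit. For platelets at Day 8 and Day 38 it is something else: the share still low among infants who were low six days before. Entry to the denominator depends on a recent value of the parameter being tabulated.

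Thrombocytopenia is the a priori safety concern (protocol sections 1.2.4.1 and 11.4), and these visits are named in the primary endpoint. With about 8 to 16 infants per group, a base of one to three infants is realistic, and one persistent low count could then print as 33% to 100%. The trigger is itself a post-vaccination outcome, so vaccine and placebo within a step are selected by an event that vaccination may change. Infants sampled routinely under Amendment 1 would enter the same rows on a different basis.

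**Working it through.** **Inputs from the documents**
- Platelets normal, mean 300,000/mm³, SD 75,000/mm³ (protocol 11.4).
- Grade 1 starts below 150,000/mm³ (SAP Table 4). This is also the lower end of the normal range used in protocol 11.4.
- About 8 or 16 infants per group (SAP Table 1 footnote).

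**Assumed, because the documents give no figure**
- Day 2 and Day 8 counts are bivariate normal with correlation ρ from 0.3 to 0.9.
- 150,000 serves as the lower normal limit, although Template 24 uses local laboratory ranges.
- The split of Template 24 by baseline category is ignored.

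**1. The plan's own figure.** Φ((50,000 − 300,000)/75,000) = Φ(−3.33) = 0.00043, or 0.04%. This reproduces the share below 50,000 stated in protocol 11.4.

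**2. Chance of a trigger with no vaccine effect.** p = Φ((150,000 − 300,000)/75,000) = Φ(−2) = 0.0228, or 2.3%. This is also the share expected below 150,000 at Day 8 if all infants were tested.

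**3. Share below 150,000 at Day 8 among triggered infants.** j/p, where j = Φ₂(−2, −2; ρ) is the probability of being low on both days.

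| ρ (assumed) | j/p | Ratio to 2.3% |
|---|---|---|
| 0 | 2.3% | 1.0 |
| 0.3 | 9.0% | 3.9 |
| 0.5 | 17.8% | 7.8 |
| 0.7 | 32.4% | 14.2 |
| 0.9 | 58.7% | 25.8 |

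The size depends on ρ. The upward direction needs only ρ above zero.

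**4. Size of the base.** Expected triggered infants: 8 × 0.0228 = 0.18 and 16 × 0.0228 = 0.36. Chance that a group has none: (1 − 0.0228)⁸ = 83% and (1 − 0.0228)¹⁶ = 69%. With no vaccine effect these rows are mostly empty, and otherwise rest on very few infants.

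**5. Mixed sampling.** Suppose k of 16 infants were tested routinely. Expected low count over expected base is [kp + (16 − k)j]/[k + (16 − k)p]. With k = 8 (assumed) the base is 8 + 8 × 0.0228 = 8.2, and the rate is 2.4% at ρ = 0.3, rising to 3.5% at ρ = 0.9. A fully conditional group gives 9% to 59% on a base of about 0.4, with the same true rate of 2.3%.

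**6. With a vaccine effect.** Let the Day 2 mean fall and recover fully by Day 8 (assumed), with ρ = 0.5 to 0.7.
- Fall of 50,000: 9.1% triggered (1.5 of 16), and 11% to 17% of these are low at Day 8.
- Fall of 110,000: 29.7% triggered (4.7 of 16), and 6% to 7% of these are low at Day 8.

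The all-infant Day 8 rate stays at 2.3% throughout. The printed percentage exceeds it in each case, but is lower for the larger Day 2 drop.

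**The case against.** **Overall occurrence is already captured.** SAP 6.4.1.1 also tabulates the maximum grade from Screening to Day 61, and Template 25 uses infants with at least one result in the period. Days 2, 31, 32 and 61 are sampled in all infants, and the drop that triggers Day 8 or Day 38 testing is itself a Day 2 or Day 32 result. This stands. A reader might infer that the haematology part of the primary endpoint is compromised as a whole; the documents do not support that.

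**No planned analysis compares these rows across doses.** The comparisons in SAP 6.4.1.2 cover Grade 2/3 adverse events, fever and related serious adverse events, each RSV group against the placebo group of its own step. SAP section 7 calls all analyses descriptive. This stands too. A reader might infer that the plan will produce a false dose trend, and could set, say, 2 of 3 (67%) in a later step against 2 of 16 (12.5%) in Step 1. Those counts are not in the documents, and the contrast needs every Step 1 infant to have been sampled routinely, which is nowhere stated. Step 6 of the working also shows that a larger transient drop lowers the conditional percentage. A misleading pattern is a risk of reading across groups, and no more than that.

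**The base is visible and the shell is illustrative.** Template 24 prints N, individual haematology is listed, and SAP section 13 allows footnotes to be adapted. The shell is also generic: it shows ALT at D2, D8, D32 and D38, when biochemistry is not scheduled. This stands only in part. A small N does not tell the reader why those infants were tested, and neither the shell nor SAP 6.4.1.1 says so.

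**Conclusion.** The point holds for the D8 and D38 rows. The platelet percentages there are conditional on a recent low count. Under the protocol's model without vaccine effect they would be expected at about 4 to 26 times the group rate (9% to 59% against 2.3%). The range rests on the assumed correlation and on bivariate normality; the upward direction rests only on a positive correlation.

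It would go too far to say that all haematology abnormality rates are inflated. For haemoglobin, leukocytes, neutrophils and the cells in Template 26 the subset is selected, but the direction depends on their relation to platelets, which the documents do not give. The number of infants sampled routinely under Amendment 1 is also not given, so how far the two regimes are mixed cannot be computed; these are the earliest infants, presumably in Step 1. This is a reporting defect in two rows on the main safety concern, worth correcting because correction costs almost nothing.

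**What to change.** In SAP section 6.4.1.1 and in the D8 and D38 rows of Templates 24 and 26:

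1. Label the results as follow-up (persistence or resolution) among infants with a platelet decrease of Grade 1 or higher on Day 2 or Day 32, and show the number triggered and the number tested.
2. Beside this, give the number of infants with an abnormal result over all vaccinated infants in the group, labelled a lower bound because untested infants are counted as not abnormal.
3. Show infants sampled routinely under Amendment 1 separately, since their results do describe an unselected set at those visits.

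Template 25 can stay as it is. The cost is a few sentences in the SAP, table footnotes and a flag for enrolment under Amendment 1. No new visits, samples or data are needed. The price is that the all-vaccinated figure understates occurrence if an untested infant had a late drop, hence the label.
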